2.3. Benefit/Risk Assessment

2.3.1. Benefits

No benefits can be guaranteed to individuals participating in this study. Participants will be contributing to research that may result in the licensure of the next generation anthrax vaccine for PEP having a more convenient dosing schedule and generating an earlier immune response than the currently licensed BioThrax vaccine.

2.3.2. Risks

The risks associated with AV7909 are similar to those described for BioThrax and CPG 7909 since AV7909 is a combination of the two products.

Since the licensure of BioThrax in 1970, more than 3.3 million individuals, primarily military personnel, have been vaccinated in the pre-exposure setting {[BioThrax.com, 2016](#)}. The safety profile of BioThrax and its associated risks are summarized in the BioThrax prescribing information {[BioThrax Prescribing Information, 2015](#)}.

CPG 7909 has been investigated clinically since the mid-1990s for indications that have included cancer monotherapy, combination use with anti-cancer therapies, and vaccine adjuvant against infectious diseases and cancers. A literature search conducted by Emergent yielded 21 completed infectious disease studies using CPG 7909 as a vaccine adjuvant in primarily healthy subjects, including the trials of the AV7909 program. These studies covered the dose range and route of administration (IM) used in the AV7909 clinical studies and are most relevant for the risk evaluation (refer to the Investigator's Brochure for details).

Hypersensitivity and Anaphylactic/Anaphylactoid Reactions

Acute allergic reactions, including anaphylaxis, have occurred with BioThrax {[BioThrax Prescribing Information, 2015](#)}. Parenteral administration of any protein product may be associated with immediate-type hypersensitivity reactions that can manifest as urticaria, shortness of breath, wheezing, nausea and cramping, and in severe cases, hypotension. In the AV7909 program, a report of urticaria after the second vaccination with AV7909 (AV7909 Arm 1; Study EBS.AVA.208) resolved with diphenhydramine hydrochloride. The subject had a history of urticaria and this event was considered by the investigator as unrelated to the study product administration. In Study EBS.AVA.201, urticaria was reported for a subject in the AV7909 Formulation 1 arm, which was treated and resolved after two days and considered possibly related to study product administration. Two subjects in Study EBS.AVA.208 discontinued vaccination because of mild generalized pruritus and rash (AV7909 Arm 2) and moderate rash (AV7909 Arm 1), all events considered to be related to study product administration. In Study V011, two subjects in the AVA + CPG 7909 arm had hypersensitivity reactions considered by the investigator to be unlikely related to study product administration; and a subject in the AVA + CPG 7909 group discontinued vaccination after the second injection due to the development of moderate generalized rash (accompanied by pruritus) that was considered to be related to study product administration. Appropriate medical treatment and supervision must be available to manage possible anaphylactic reactions following administration of the vaccine.

BioThrax and AV7909 vaccine are not to be administered to subjects with known sensitivity to any of the vaccine components, eg, synthetic ODNs, formaldehyde, benzethonium chloride (phemerol), or aluminum.

Additionally, as the stopper of the vials for BioThrax vaccine contains natural rubber latex and may cause allergic reactions in latex-sensitive individuals, BioThrax is not to be administered to subjects with latex allergy.

Adverse Events of Autoimmune Etiology

There is a potential for CpG ODN adjuvants to trigger autoimmune disease in susceptible individuals {[Segal et al 2000](#)}, possibly as a result of non-specific activation of T or B lymphocytes. No subjects in the completed AV7909 clinical trials have reported AEs related to autoimmune disorders. Additionally, no AEs suggestive of autoimmune disease have been reported in the reviewed published data on the CPG 7909-adjuvanted infectious disease vaccine trials. A number of these trials reported subjects with moderate, transient elevations above the normal range in anti-double stranded deoxyribonucleic acid (anti-dsDNA) values or positive antinuclear antibody (ANA) or mild elevations in rheumatoid factor (RF) following vaccination, which typically returned to normal by the next dose or end of the study and were not associated with clinical symptoms {[Ellis et al, 2010](#); [Mullen et al, 2008](#); [Cooper et al, 2005](#); [Cooper et al, 2004](#)}. In a phase 3 trial of Heplisav-B vaccine containing a different CpG ODN, CpG 1018, in subjects followed for 13 months after the first dose of vaccine, the incidences of new onset immune-mediated AEs (as reviewed by independent adjudicators) were not clinically different between the Heplisav-B group (0.1%; 4/5587) and the non-adjuvanted Energix-B group (0%; n=2781), nor were these AEs in the Heplisav-B group considered related to vaccination {[Heplisav-B Prescribing Information, 2017](#)}.

In oncology trials of CPG 7909 that typically have used higher doses and treatment durations than expected with AV7909 vaccine exposure (refer to the Investigator's Brochure for more details), autoimmune disease has been reported in multiple subjects, although causal attribution to the study product is complicated by comorbidities and concomitant products/therapies. The autoimmune conditions observed have included polyarthralgia, arthritis, Sjögren's Syndrome, autoimmune thyroiditis, vitiligo, Guillain-Barré syndrome, and ulcerative colitis.

Because of this potential risk, the enrollment of individuals with a history of autoimmune disorders or active autoimmune disease will be prohibited in the current trial. Additionally, because of the possibility for a delay between the vaccination and onset of symptoms indicative of a disease process, all participants will be followed for potential adverse events of autoimmune etiology up to Month 13 (nominally for 12 months after the last vaccination). Such AEs will be captured as "adverse events of special interest [AESI]" referring to the list of autoimmune disorders compiled by CBER and listed in [Appendix B](#). Blood samples will be collected at specified time points from all participants for auto-antibody testing. Participants who discontinue study treatment will be encouraged to attend all subsequent clinic visits and safety follow-up contacts to facilitate this monitoring.

Pregnancy and Lactation

No reproductive toxicity studies have been performed with AV7909. BioThrax can cause fetal harm when administered to a pregnant woman {[BioThrax Prescribing Information, 2015](#)}. CPG 7909 had been determined to be embryo-lethal in rabbits and teratogenic in developing rats and rabbits at doses far in excess of the individual vaccination dose for anthrax PEP (0.25 mg). In rats, fetal skeletal anomalies were noted (>3 mg/kg/day); in rabbits, slightly reduced numbers of viable fetuses (3 mg/kg/day), and external, visceral, and skeletal malformations occurred (>1 mg/kg/day).

Consequently, breastfeeding and a positive pregnancy test will preclude study enrollment. All women of childbearing potential must additionally have a negative pregnancy test before each vaccine administration, and must use effective contraception from at least one month prior to Day 1 and continued through Month 13. Confirmed pregnancy will result in discontinuation of vaccinations. Participants must be monitored for pregnancy outcomes according to protocol-specified procedures.

Injections

Potential risks associated with both IM and SC injections include nerve or blood vessel damage, dizziness, fainting, infection, sterile abscess, and pain associated with a needle stick. Potential risks associated with venipuncture include pain/tenderness, swelling, bleeding, bruising, dizziness, and infection.

Refer to the Investigator's Brochure for further details.

3. STUDY OBJECTIVES AND ENDPOINTS

3.1. Study Objectives

Study objectives are as follows:

Primary:

- To demonstrate lot consistency following a two-dose schedule of AV7909 (Days 1 and 15) administered IM in healthy adults.
- To demonstrate immunogenicity under the US FDA's Animal Rule on Day 64 following a two-dose schedule of AV7909 (Days 1 and 15) administered IM in healthy adults.
- To demonstrate immunogenicity using the US FDA's Animal Rule at Day 64 based on the noninferiority of a two-dose schedule of AV7909 (Days 1 and 15) administered IM to the licensed three-dose schedule of BioThrax (Days 1, 15, and 29) administered SC in healthy adults.
- To evaluate the safety of AV7909 in healthy adults following a two-dose schedule (Days 1 and 15) administered IM.

Secondary:

- To demonstrate immunogenicity under the US FDA's Animal Rule on Day 29 following a two-dose schedule of AV7909 (Days 1 and 15) administered IM in healthy adults.

3.2. Study Endpoints

3.2.1. Primary Endpoints

The primary study endpoints are as follows:

Lot Consistency:

- Equivalent immunogenicity across three consecutive AV7909 lots as demonstrated by the 95% CI for the ratios of geometric mean TNA NF₅₀ at Day 64 for each of the three lot-to-lot comparisons to be within 0.5 and 2.0.
- Protective level of immunogenicity in all three consecutive AV7909 lots as demonstrated by the LB of the two-sided 95% CI to be $\geq 40\%$ for the proportions of AV7909 subjects in each of the three lots achieving a TNA NF₅₀ ≥ 0.56 at Day 64.

Immunogenicity:

- Lower bound of the two-sided 95% CI is $\geq 40\%$ for the proportion of AV7909 participants in Groups 1-3 (three lots pooled) achieving a TNA NF₅₀ ≥ 0.56 on Day 64.

- Non-inferiority of AV7909 to BioThrax at Day 64 as determined by the two-sided lower 95% CI of the difference in the proportion of AV7909 participants (three lots pooled) with a TNA NF₅₀ ≥ 0.29 and the proportion of BioThrax participants with a TNA NF₅₀ ≥ 0.29 being greater than -15%.

Safety:

- Incidences of SAEs from the time of the first vaccination on Day 1 through the 12-month safety follow-up telephone call following the last vaccination.

3.2.2. Secondary Endpoints

The secondary study endpoints are as follows:

Immunogenicity:

- Lower bound of the two-sided 95% CI will be ≥ 67% for the proportion of AV7909 participants in Groups 1-3 (three lots pooled) achieving a TNA NF₅₀ ≥ 0.15 on Day 29.

Safety:

- Incidences of AEs from the time of the first vaccination on Day 1 through Day 64
- Incidences of clinical laboratory abnormalities
- Incidences of autoimmune-associated AESIs from the time of the first vaccination on Day 1 through the 12-month safety follow-up telephone call following the last vaccination
- Incidences of solicited systemic reactions and solicited injection site reactions by severity following each vaccination as reported in participant e-diaries

4. STUDY DESIGN

4.1. Overall Study Design

This is a phase 3, multicenter, randomized, double-blind, parallel-group trial designed to evaluate the lot consistency (using three consecutive lots), immunogenicity, and safety of a two-dose schedule of AV7909 (Days 1 and 15) administered IM in healthy adults for an indication of PEP of anthrax.

Healthy adults between 18 and 65 years of age (inclusive) will sign and date an informed consent form and then be screened for eligibility for participation in the study 2 to 28 days prior to randomization. Participants meeting the entry criteria will be randomized 2:2:2:1 (block size of 7) to one of four study groups on Day 1, as shown in [Table 2](#). Randomization will be stratified by site. Racial distribution will be monitored among recruited participants. Participants who are randomized and do not receive vaccination on the same day will be withdrawn from the study.

Table 2: Study Groups

Group No./Treatment	Sample Size (N)	Day 1	Day 15	Day 29
1/AV7909 Lot 1	1100	AV7909 Lot 1 (IM)	AV7909 Lot 1 (IM)	Placebo (SC)
2/AV7909 Lot 2	1100	AV7909 Lot 2 (IM)	AV7909 Lot 2 (IM)	Placebo (SC)
3/AV7909 Lot 3	1100	AV7909 Lot 3 (IM)	AV7909 Lot 3 (IM)	Placebo (SC)
4/BioThrax	550	BioThrax (SC)	BioThrax (SC)	BioThrax (SC)
Total	3850			

IM = intramuscular injection in the deltoid muscle; SC = subcutaneous injection over the deltoid region.

The study schematic is provided in [Figure 1](#).

Blood samples for immunogenicity testing will be collected prior to vaccination on Day 1 (baseline) and on Days 29 and 64 and assayed using toxin neutralization assay. The assay results will be reported as the reciprocal of a serum sample dilution that results in 50% neutralization of cytotoxicity of the lethal toxin (50% effective dilution; ED₅₀). To standardize assay results, the results will be divided by the ED₅₀ of a serum reference standard, and the resulting ratio will be reported as a 50% neutralization factor (NF₅₀).

[figure not shown]
Participants will be evaluated for safety through Day 64 (or the early withdrawal visit [EWV]), as assessed by clinical laboratory tests (hematology, serum chemistry, and urinalysis), monitoring of AEs including SAEs and AESIs, vital signs, and physical examinations (PEs). Adverse events of special interest are AEs associated with autoimmune disease as defined by the Center for Biologics Evaluation and Research [CBER]; refer to [Appendix B](#)), and might represent a safety signal for vaccine-associated autoimmunity. The severity of AEs, laboratory test results for select analytes, and vital sign results will be assessed based on the FDA Guidance for Industry: *Toxicity Grading Scale for Healthy Adult and Adolescent Volunteers Enrolled in Preventative Vaccine Clinical Trials* (refer to [Appendix A](#)). Reactogenicity (solicited systemic and injection site reactions) will be assessed daily by the participants using e-diaries for at least seven days after each vaccination. If

injection site or systemic reactions continue beyond seven days, participants will be prompted to continue e-diary entries until resolved for at least two consecutive days. Use of medications will be collected at each study visit. In addition, blood samples for auto-antibody assessment will be taken at Day 1 predose and Day 64 (or EWV) for testing for rheumatoid factor (RF), antinuclear antibody (ANA) and anti-double stranded deoxyribonucleic acid (dsDNA) antibodies, and thyroid-stimulating hormone (TSH). To ensure a robust safety follow up, participants who receive at least one dose of vaccine but for any reason discontinue vaccinations prematurely will be asked to participate in the further planned study visits up to Day 64 for safety assessment only.

Participants who receive at least one dose of vaccine will also participate in safety follow-up phone calls occurring on Day 43, Month 4 (Day 120), Month 7 (Day 211), Month 10 (Day 302), and Month 13 (Day 394); ie, nominally 0.5, 3, 6, 9, and 12 months after the last vaccination to collect information on AEs, SAEs and any potential AESIs. Based on responses at these phone contacts, participants may be asked to return to the clinic for an unscheduled visit to provide blood samples for auto-antibody testing to investigate potential AESI reports.

Independent safety oversight will be provided by a Data Safety Monitoring Board (DSMB), which will be notified of significant AEs (refer to [Section 8.4.1](#)) as determined by the MM on an ongoing basis. The DSMB will comprise at least three voting members, to include one expert in immunology to specifically support the evaluation of potential AESIs for autoimmune etiology, if pre-existing or new onset, and relationship to the study product. A planned interim DSMB safety data review will be conducted after the first 500 participants have completed the Day 29 visit, comprising all safety evaluations through two weeks after the second vaccination. All DSMB reviews will be performed with blinded data, unless otherwise requested by the DSMB Chair. The DSMB will make recommendations regarding the safety of continuing enrollment and dosing. Study enrollment and dosing may be interrupted at the request of the DSMB Chair if it is believed that an AE represents a significant safety concern requiring suspension of dosing pending full DSMB evaluation. The operations of the DSMB will be detailed in a DSMB Charter.

Figure 1: Study Design Schematic

IM = intramuscular; SC = subcutaneous.
AV7909 is administered IM on Days 1 and 15, with placebo administered SC on Day 29.
BioThrax is administered SC on Days 1, 15, and 29.

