Healthy adults between 18 and 65 years of age (inclusive) will sign and date an informed consent form and then be screened for eligibility for participation in the study 2 to 28 days prior to randomization. Participants meeting the entry criteria will be randomized 2:2:2:1 (block size of 7) to one of four study groups on Day 1, as shown in the table below. Randomization will be stratified by site. Racial distribution will be monitored among recruited participants. Participants who are randomized and do not receive vaccination on the same day will be withdrawn from the study.

Study Groups

Group Number	Sample Size	Day 1	Day 15	Day 29
1	1100	AV7909 Lot 1 (IM)	AV7909 Lot 1 (IM)	Placebo (SC)
2	1100	AV7909 Lot 2 (IM)	AV7909 Lot 2 (IM)	Placebo (SC)
3	1100	AV7909 Lot 3 (IM)	AV7909 Lot 3 (IM)	Placebo (SC)
4	550	BioThrax (SC)	Biothrax (SC)	BioThrax (SC)
Total	3850			

IM = intramuscular injection in the deltoid muscle; SC = subcutaneous injection over the deltoid region.

Blood samples for immunogenicity testing will be collected prior to vaccination on Day 1 (baseline) and on Days 29 and 64 and assayed using toxin neutralization assay. The assay results will be reported as the reciprocal of a serum sample dilution that results in 50% neutralization of cytotoxicity of the lethal toxin (50% effective dilution; ED₅₀). To standardize assay results, the results will be divided by the ED₅₀ of a serum reference standard, and the resulting ratio will be reported as a 50% neutralization factor (NF₅₀).

Participants will be evaluated for safety through Day 64 (or the early withdrawal visit [EWV]), as assessed by clinical laboratory tests (hematology, serum chemistry, and urinalysis), monitoring of adverse events (AEs) including serious adverse events (SAEs) and adverse events of special interest (AESIs), vital signs, and physical examinations (PEs). Adverse events of special interest are AEs associated with autoimmune disease as defined by the Center for Biologics Evaluation and Research [CBER]), and might represent a safety signal for vaccine-associated autoimmunity. The severity of AEs,

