5. STUDY POPULATION

Participants will be recruited at approximately 40 clinical research sites in the US. A total of 3850 healthy adults meeting the eligibility criteria will be randomized to one of the four treatment groups.

No waivers of inclusion and/or exclusion criteria will be permitted in the trial. Racial distribution will be monitored among recruited participants.

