6.3.2. Blinding

The site pharmacists or other designated, licensed study personnel who will prepare and/or administer the vaccinations will be unblinded to IP assignment. These individuals must be licensed to administer medication/vaccination and will not be involved with participant evaluations, nor will they engage in other study activities that could reveal the blind or introduce bias in the study data.

Principal investigators (PIs), all investigational site staff (except those responsible for preparing/administering the IP), representatives of the Sponsor (except unblinded study monitor[s] and unblinded Quality Assurance representative[s]), representatives of Biomedical Advanced Research and Development Authority (BARDA), CRO staff (except unblinded

statistician and unblinded study monitor[s]), and all participants enrolled in this study will be blinded to the IP assignment. To facilitate study oversight while preserving the study blind, a minimum number of CRO and Sponsor personnel will have access to treatment randomization information. The unblinded CRO statistician will have access to the treatment assignment information in the IxRS to support the activities of the DSMB. During monitoring visits, an unblinded CRO study monitor will check that the blind has been maintained properly and will review IP accountability records. Oversight of this activity will be facilitated by the Sponsor's unblinded study monitor(s). Blinded CRO study monitors will continuously assess the progress of the study, but not have access to the unblinded pharmacy records. Individuals with access to the treatment assignment details will not share the identifying information with blinded personnel while the study blind is in effect.

Under certain circumstances (eg, safety reasons, required reporting to regulatory agencies), unblinding of IP for a particular participant will be allowed. Otherwise, unblinding of the study will only occur after the clinical database has been locked. Refer to [Section 9.5](#) for procedures on how to break the blind for individual participants or procedures in case of accidental participant unblinding. Refer to the Pharmacy Manual for procedures in case of accidental unblinding of study-affiliated personnel (Sponsor, CRO, BARDA).

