2.5 Randomization and Blinding

2.5.1 Randomization

At the Day 1 (randomization) visit, after the PI has confirmed that the participant meets all of the inclusion criteria and none of the exclusion criteria, the participant will be randomly assigned to one of the four study groups with the ratio of 2:2:2:1 (block size of 7) via an interactive voice and/or web response system (IxRS). Randomization will be stratified by site. Racial distribution will be monitored among recruited participants. Participants who are randomized and do not receive vaccination on the same day will be withdrawn from the study. Randomized participants who withdraw from the study for any reason will not be replaced in this trial.

A randomization plan describing the method of treatment allocation and implementation of this method will be prepared and finalized prior to randomization of the first participant.

A screen failure is a participant from whom informed consent is obtained and documented in writing, but who is not subsequently randomized to study treatment. Participants who are screen failures are permitted to be rescreened one time (only) according to the PI's discretion. If a participant is rescreened, a new subject ID will be assigned. To link records to the same participant, the participant's previous subject ID will be recorded in the eCRF along with the new subject ID. Participants who complete the rescreening and are randomized in the study will not be considered screen failures.

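### The protocol and SAP disclose one fixed block of 7 within site, so a single unblinded BioThrax participant identifies all six block-mates as AV7909 (minor, cheap to improve)

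*Protocol*

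**What the plan says.** Under Protocol 4.1, eligible participants are "randomized 2:2:2:1 (block size of 7") on Day 1. The protocol synopsis prints the same ratio and block size. SAP 2.5.1 repeats them, "with the ratio of 2:2:2:1 (block size of 7) via an interactive voice and/or web response system (IxRS"). Protocol 4.1 adds: "Randomization will be stratified by site". Site is the only stratification factor, and no second or varying block size appears anywhere.

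Protocol 6.3.1 and SAP 2.5.1 both assign the allocation method to a separate randomization plan, which is not among the documents. Protocol 6.3.1 and SAP 2.2.1 describe the randomization without giving the block size.

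On blinding, Protocol 6.3.2 says that the site personnel who prepare or give injections "will be unblinded to IP assignment", and it keeps them out of participant evaluations. Protocol 6.1.2 and 6.2.3 require a segregated injection area and a masked syringe barrel. Under 6.1.2 the participant looks away and a blinded staff member does the post-injection observation. Protocol 9.6 allows the code to be broken for a life-threatening emergency or pregnancy, and in special circumstances such as SUSARs or safety signals. It also provides for accidental unblinding.

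**The concern.** Because the block size equals the sum of the ratio, the composition of each block is fixed at the level of individual participants: two from each lot and one BioThrax. Anyone with the protocol and the order of Day 1 visits at a site can count in sevens. Randomized participants who withdraw are not replaced (Protocol 6.3.1), so withdrawals do not disturb the count.

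Breaking one code should reveal one assignment. Here, breaking a BioThrax code reveals seven. Order within the block does not matter for this, and participants are followed to Month 13, so one late unblinding can expose six people still under observation whose own codes were never broken.

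The judgements at stake are those made by the blinded investigator:

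- causality (Protocol 9.2.2);
- confirmation of Grade 3 or higher systemic reactions, and relatedness decisions that stop vaccination (Protocol 7.3.1, Table 5);
- whether a Grade 3 solicited reaction is serious (Protocol 8.3.5.1).

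SAE incidence is the primary safety endpoint and is reported as a relative risk against BioThrax (SAP 7.2.3).

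**Working it through.** **Inputs.** Ratio 2:2:2:1, block 7, strata = sites (Protocol 4.1, SAP 2.5.1). Protocol 5 gives the total: "A total of 3850 healthy adults meeting the eligibility criteria will be randomized to one of the four treatment groups". Sites: about 40 (Protocol 5) or 30 to 40 (SAP 4.7).

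**Step 1: reproduce the planned group sizes.** 3850 / 7 = 550 blocks. 550 × 2 = 1100 per lot and 550 × 1 = 550 BioThrax, which matches Table 2. At 40 sites this is 3850 / 40 = 96.25 participants, or 13.75 blocks, per site. At 30 sites it is 128.3 participants, or 18.3 blocks. Only a last, unfilled block at a site can lack its BioThrax participant.

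**Step 2: what one known assignment reveals about the other six in its block.**

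| What is known | Chance that another given block-mate is on AV7909 |
|---|---|
| Nothing | 6/7 = 85.7% |
| One AV7909 participant, block of 7 | 5/6 = 83.3% |
| One BioThrax participant, block of 7 | 6/6 = 100% |
| One BioThrax participant, known block of 14 | 12/13 = 92.3% |

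Only a BioThrax unblinding gives certainty, and BioThrax participants are 1 in 7. An AV7909 unblinding tells almost nothing. A larger block removes the certainty, and an undisclosed mix also hides where a block starts and ends.

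**Step 3: average guessing accuracy when all earlier assignments in the block are known.** Always guessing AV7909 gives 6 of 7 right (85.7%). Knowing the block helps only when BioThrax falls last (probability 1/7), when all 7 are right. Otherwise 6 are right. The expected number is 6 × 6/7 + 7 × 1/7 = 43/7 = 6.14 of 7, or 87.8%. The gain is about 2 percentage points.

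**Step 4: assignments certain before they are made, given all earlier ones.** This is the expected length of the final run of one vaccine. For a block with V AV7909 and B BioThrax it is V/(B+1) + B/(V+1).

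- Block of 7: 6/2 + 1/7 = 22/7 = 3.14 (44.9%)
- Block of 14: 12/3 + 2/13 = 4.15 (29.7%)
- Block of 21: 18/4 + 3/19 = 4.66 (22.2%)

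For the exact group in a block of 7 (each lot and BioThrax separately), the sum is 3 × 2/6 + 1/7 = 8/7 = 1.14, or 16.3%. Enumerating all 630 orderings of the block of 7 gives the same 22/7 and 8/7.

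**Step 5: enrolment or assessment?** Study duration of about 20 months less about 15 months per participant suggests about 5 months of accrual (an assumption; range 4 to 6). With equal accrual over 40 sites, a block fills in 7 / (96.25/5) × 30.4 = 11 days (range 9 to 13). Most unblindings would therefore come after the block is full. That makes assessment during follow-up, not selection at enrolment, the main exposure.

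**The case against.** The strongest reply is that a blinded assessor has no planned way to recognise a BioThrax participant. A reader might infer from the IM and SC routes on Days 1 and 15 that site staff can see who received what. The documents do not support that: the area is segregated, the syringe is masked, and vaccinators take no part in assessment. Day 29 is SC in every group. Protocol 4.3 describes injection-site reactions with the chosen formulation as similar to those with BioThrax. The unblinded preparers know each assignment whatever the block size, so mixed blocks do not change what they could disclose about people already treated. This reply stands, and it makes the concern conditional on an unblinding or a correct inference.

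Second, much of the safety data is protected in other ways. SAEs are recorded regardless of causality, laboratory grades come from the central laboratory, participants grade reactions in the e-diary, potential AESIs go to a blinded DSMB expert, and no safety hypothesis is tested. This also stands and narrows the exposure to the investigator judgements listed above.

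Third, block choice is a design preference, and the randomization plan might differ from the printed text. The plan cannot be checked. However, the protocol and SAP agree on 7, and nothing in either conceals it. Protocol 9.6 itself foresees both formal and accidental unblinding, so the condition is not remote.

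**Conclusion.** The point holds as a minor improvement. Its size is six additional participants identified for each BioThrax participant unblinded, with certainty rising from 85.7% to 100%. Across a block, the average gain in guessing is about 2 points. Discontinuation decisions are exposed only if the unblinding comes before the Day 29 injection; causality and seriousness judgements are exposed for the rest of follow-up.

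Two stronger readings should be resisted. A reader might take the 44.9% in Step 4 as the share of assignments exposed to biased assessment. It measures predictability at enrolment for someone who already knows every earlier assignment, and the plan gives no blinded person that knowledge. A reader might also infer that the immunogenicity conclusions are at risk. TNA is a laboratory assay, and the exact group is predictable in only 16.3% of assignments even under full prior knowledge, so lot consistency and non-inferiority are essentially unaffected.

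The conclusion assumes that the list was generated as printed, in consecutive blocks of 7 within site, and that site staff know the order of randomization.

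**What to change.** 1. Generate the list with randomly mixed block sizes within site, for example 7 and 14. The ratio and the planned 1100/1100/1100/550 do not change.
2. Delete the block size from the protocol synopsis, Protocol 4.1 and SAP 2.5.1. State there only the ratio and stratification by site, and hold the block sizes in the restricted randomization plan.
3. Randomization appears to have started: SAP 4.9.2 describes four people enrolled twice, and Appendix IV says that they received all three vaccinations at their first enrolment. Mixed blocks can therefore apply only to lists not yet issued, and deleting the phrase cannot restore concealment at sites that already hold the protocol.
4. For blocks already used, have the unblinded statistician list every formal or accidental unblinding of a BioThrax participant before database lock and identify the block-mates. The study report should state whether any investigator judgements on those block-mates were made after the unblinding date.

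Cost: one setting for any new list, three text deletions and one listing. The statistical downside is slightly looser balance within small sites, which matters little because SAP 4.7 plans no site-adjusted tests.
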